15.6 Correlative Studies

Tumor cell apoptotic index: Apoptosis studies based on the TUNEL assay conducted in the context of the IMPACT study showed that the rate of apoptosis actually *declined* after two weeks of anastrozole treatment when the percentage TUNEL positive cells was less than one percent, with an SD of less than one percent [12]. Given the very low background of TUNEL positivity, a modest sized study is sufficient to demonstrate an increase in cell death. We will use the TUNEL assay to assess apoptosis at baseline and in the sample taken on PD 0332991. The TUNEL-positive cells will be counted using the point counting approach used for Ki67 and the apoptosis index will be calculated as the number of positive cells divided by the number of all cells and multiplied by 100.

Steady state levels of estradiol: Steady state levels of estradiol on serially collected serum samples will be examined in premenopausal women to confirm the efficacy of the

anastrozole goserelin therapy in suppressing both ovarian and peripheal estradiol production. The change of estradiol level over time will be described by summary statistics and also compared using 2-way ANOVA for repeated measurement data

Pharmacodynamic markers and markers of tumor cell senescence: The pharmacodynamic effect of PD 0332991 in combination with anastrozole on RB phosphorylation and markers of senescence will be assessed by phosphoproteomics and immunohistochemistry analysis on serial tumor biopsies. The change of RB phosphorylation and senescence markers over time will be described by summary statistics and also compared using 2-way ANOVA for repeated measurement data.

Explore potential markers of sensitivity and resistance: In preclinical studies, RB proficient cell lines with low p16 expression were found to be most sensitive to PD 0332991 in ovarian cancer. In addition, copy number variations of CDKN2A, RB, CCNE1, CCND1 were associated with response [102]. Therefore, tumor specimens collected on Cycle 1 day 1 will be analyzed for the protein expression of these genes by immunohistochemistry. Gene copy number changes will be assessed by circular binary segment (CBS) analysis using Signal Map Software (Nimblegen, Madison, WI, USA) and its association with clinical outcomes will also be assessed using contingency tables and fisher's exact test. The gene expression levels between responses will also be summarized using means, standard deviations, medians, and compared by t-test or Mann-Whitney rank-sum test as appropriate.

To assess the concentrations of anastrozole and PD 0332991: The concentrations of anastrozole prior to and 90 minutes following anastrozole (without PD 0332991) on Cycle 1 Day 1, as well as the concentrations of anastrozole prior to and 90 minutes following both anastrozole and PD 0332991 on Cycle 1 Day 15 will be summarized using means and standard deviations, and the differneces will be compared using two-way ANOVA for repeated measurement data. Data transformation will also be performed as necessary to better satisfy normality assumption. Similar analysis will be performed for the concentration of of PD 0332991.

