1.3 Cyclin D/Cdk4/6 Pathway in ER+ Breast Cancer

1.3.1 Interaction of Estrogens and Cyclin-Dependent Kinases in Breast Cancer Cells

Studies of ER-positive breast cancer cell lines indicate that estrogens[34] and antiestrogens[35] act on sensitive populations of cells in early to mid-G1 phase. G1/S transition is under the control of cyclin-dependent kinases (Cdks) activated by specific complex formation with regulatory cyclins. Cdk4 and Cdk6 are activated by binding to D-type cyclins and act early in G1 phase[36-39]. A primary target of Cdk action in G1 phase is the retinoblastoma susceptibility gene product (pRb), which mediates G1 arrest through sequestration of transcriptional factors of the E2F-DP family. Phosphorylation of pRb and other members of the pocket protein family (p107 and p130) by active cyclin-Cdk complexes leads to release of E2F and DP transcription factors and transcription of requisite genes for S-phase entry[39]. D-type cyclins play an essential role in recognition of extracellular growth stimuli and initiation of G1 transit[40, 41], and several lines of evidence have linked estrogen regulation of cellular proliferation to cyclin D1 expression. Estrogen-induced proliferation of normal uterine and breast epithelium in vivo is associated with increased expression of cyclin D1 mRNA and protein[42-45]. Expression of cyclin D1 in breast tumor isolates correlates with ER-positive

status[46-48]. MCF-7 breast cancer cells treated with estrogen exhibit increased expression of cyclin D1 mRNA and protein, formation of active cyclin D1-Cdk4 complexes, and phosphorylation of pRb leading to G₁/S transition[49-52]. Estrogen-induced S-phase entry in these cells is inhibited by microinjection of antibodies to cyclin D1[53]. Antiestrogen-induced growth arrest of ER-positive breast cancer cells is associated with decreased cyclin D1 expression[54]. Collectively, these studies are consistent with a model of estrogen action in which receptor activation induces increased cyclin D1 expression, Cdk4 activation, and cell cycle progression. An upstream role for cyclin D1 has been suggested by recent reports describing direct physical interactions between cyclin D1 and the ER, leading to recruitment of steroid receptor coactivators and activation of ER-dependent transcription. This occurs in the absence of hormone and is independent of D cyclin association with Cdk4 [55-58].

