1.9.4 To Assess Effect of PD 0332991 on Markers of Tumor Cell Senescence

Studies in preclinical models of ER+ breast cancer indicated that PD 0332991 induced stable cell cycle arrest that was fundamentally distinct from those elicited by ER antagonists and was capable of inducing aspects of cellular senescence, as measured by expression of senescence-associated b-galactosidase [20]. In addition, candidate proteins important for senescence including p16, IL6, cyclin D1, activated mTOR (such as pS6), FOXM1 phosphorylation, will be examined [19, 101]. These markers will be assayed on tumors collected at all time points. Since surgery occurs after at least 3 weeks after the last dose of PD 0332991, a comparison of these markers as well as Ki67 level between surgery and C1D15 sample will be informative in determining whether 4 months of combination therapy induced irreversible cell cycle arrest and cells have entered senescence.

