1.9.5 Evaluation of Target Inhibition on the Cdk4/6-Rb Pathway

The pharmacodynamic effect of PD 0332991 in combination with anastrozole on the Cdk4/6-Rb pathway activities will be assessed by phosphoproteomics and immunohistochemistry analysis on serial tumor biopsies. Since PD 0332991 inhibits Cdk4/6 phosphorylation of Rb at Ser^{801/811} and Ser⁷⁸⁰, the levels of total and phosphorylated RB will be examined at baseline, post 1 cycle of single agent anastrozole, then post 2 weeks of PD 0332991 in combination with anastrozole.

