2.3 Exploratory Objectives

The following objectives will be assessed in PIK3CA mutant cohort and in PIK3CA WT cohort combined or separately, and assessed separately in the endocrine resistant cohort.

1. To assess tumor cell apoptosis index and senescence markers on serially collected tumor specimens
2. To examine the pharmacodynamic effect of PD 0332991 in combination with anastrozole using serially collected tumor specimens (baseline, C1D1, 2 weeks on combination therapy, and surgery)
3. To explore molecular mechanisms which could affect tumor response to the combination PD 0332991 and anastrozole by tumor genomic, transcriptomic, and proteomic analysis
4. To document pathologic staging (tumor size, lymph node status) following neoadjuvant chemotherapy in patients who had tumor Ki67>10% on C1D15 and elected to receive neoadjuvant chemotherapy
5. To explore circulating markers predictive of cancer recurrence.
6. To assess the concentrations of anastrozole prior to and 90 minutes following anastrozole (without PD 0332991) on Cycle 1 Day 1 and to compare these concentrations to the concentrations of anastrozole prior to and 90 minutes following both anastrozole and PD 0332991 on Cycle 1 Day 15.
7. To assess the concentration of PD 0332991 prior to and 90 minutes following both

anastrozole and PD 0332991 on Cycle 1 Day 15.

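### In the two PIK3CA cohorts, the repeated-measures ANOVA over time for RB phosphorylation and senescence markers can be significant from the anastrozole run-in alone, so its time effect is not evidence of a PD 0332991 effect

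*Combined protocol and SAP*

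**What the plan says.** Section 15.6 gives the purpose: "The pharmacodynamic effect of PD 0332991 in combination with anastrozole on RB phosphorylation and markers of senescence will be assessed". The only inferential method it names for these markers, a repeated-measures analysis, is the one in "The change of RB phosphorylation and senescence markers over time will be described by summary statistics and also compared using 2-way ANOVA". It does not name the two factors, the time points or any contrast.

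The time points have to be collected from other sections:

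- Exploratory objective 2 (section 2.3) works "using serially collected tumor specimens (baseline, C1D1, 2 weeks on combination therapy, and surgery".
- Section 1.9.5 lists three times for total and phosphorylated RB: "examined at baseline, post 1 cycle of single agent anastrozole, then post 2 weeks of PD 0332991 in combination with anastrozole". Surgery is not listed there.
- Section 1.9.4 says of the senescence markers: "These markers will be assayed on tumors collected at all time points". It also mentions a comparison of surgery with C1D15, to judge whether arrest is reversible.

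In the PIK3CA cohorts, section 5.1 puts a 28-day Cycle 0 of anastrozole (with goserelin if premenopausal) between baseline and C1D1. Section 10.1 allows up to 42 days. In the endocrine resistant cohort, section 9.1.3 schedules tumor samples only before PD 0332991, at C1D15 and at surgery. Section 15.5 analyses cohorts separately unless otherwise specified.

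**The concern.** The question is what PD 0332991 adds. The title of section 1.9.4 puts it that way: "To Assess Effect of PD 0332991 on Markers of Tumor Cell Senescence". The comparison that bears on it is C1D15 (combination) against C1D1 (anastrozole alone). The null of an overall time test is different: it says the marker mean is the same at every visit, including the one before any anastrozole.

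The protocol gives reasons to doubt that null even if PD 0332991 is inert. Section 1.3.1 describes estrogen raising cyclin D1 and driving pRb phosphorylation, and states: "Antiestrogen-induced growth arrest of ER-positive breast cancer cells is associated with decreased cyclin D1 expression". Cyclin D1 is on the senescence list in sections 1.9.4 and 9.4.3.

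Section 1.1 makes induction of senescence part of the trial's goal. What is at stake is a mechanistic claim: a significant time effect could be read as target inhibition or senescence caused by PD 0332991 when anastrozole produced it.

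**Working it through.** The plan gives no alpha, power, SD or effect size for this analysis, so there is no figure of its own to reproduce. The behaviour of an overall time test can be computed instead.

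**Inputs from the documents.** n=28 (wild type) and n=15 (mutant) are the numbers evaluable for C1D15 Ki67 in section 1.8. n=33 is the planned wild type size in section 15.3. There are four times under objective 2.3(2), or three for RB under section 1.9.5.

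**Assumptions.**
- Every evaluable woman has the marker at every time.
- The test is two-sided at 5%, with factors patient and time.
- The within-woman error SD σ is constant, so the SD of a paired difference is √2·σ.
- The run-in shifts the marker by d SDs of the paired difference (δ = d·√2·σ). The shift is complete by C1D1 and flat afterwards.
- The PD 0332991 effect is zero.

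**Formula.** The time F statistic on k times has k−1 and (n−1)(k−1) degrees of freedom and noncentrality λ = n·Σ(τ_j − mean τ)²/σ².

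- Four times, means (0, δ, δ, δ): the sum of squares is 0.75δ², so λ = 1.5·n·d².
- Three times, means (0, δ, δ): the sum of squares is (2/3)δ², so λ = (4/3)·n·d².

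Example: n=28, d=0.5 and four times give λ = 1.5 × 28 × 0.25 = 10.5 on 3 and 81 df, and a rejection probability of 0.761.

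**Rejection by the time test with no PD 0332991 effect, four times**

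| d | n=15 | n=28 | n=33 |
|---|---|---|---|
| 0 | 5% | 5% | 5% |
| 0.25 | 14% | 23% | 27% |
| 0.5 | 45% | 76% | 84% |
| 0.75 | 82% | 99% | >99% |

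With three times at n=28, the rates for d = 0.25, 0.5 and 0.75 are 25%, 76% and 98%, so leaving surgery out for RB changes little. A simulation of 20,000 runs per setting agrees with the four-time figures at d = 0, 0.5 and 0.75 (for example 0.760 at n=28, d=0.5). In the same runs the paired C1D15 minus C1D1 test rejects 4.8% to 5.2% of the time, whatever the run-in shift.

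**The p-value cannot tell the two sources apart.** Means of (0, δ, δ, δ), run-in only, and (0, 0, δ, 0), a PD 0332991 change seen only at C1D15, have the same sum of squares, 0.75δ². Both give 76% at n=28, d=0.5.

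**Power of the contrast.** For a PD 0332991 change of 0.5 SD, the paired test has 72% power at n=28, 80% at n=33 and 44% at n=15. The time test has 76% at n=28 if the change is seen at C1D15 only. If the change persists to surgery, the sum of squares is δ², λ = 2 × 28 × 0.25 = 14, and the time test has 88%.

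**Endocrine resistant cohort.** With the three scheduled times and no change, simulated rejection is 5.0% at n=12 and 4.9% at n=37. There is no run-in to inflate it.

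**The case against.** The strongest reply is that section 15.6 does not say the overall time p-value will be the evidence. It names no null, it also plans summary statistics, and within-woman contrasts are ordinary output of a repeated-measures model. On that view the defect is only an unnamed contrast. Part of this stands: it would be an inference that the investigators will report the time effect as target inhibition. But the only inferential comparison written down is change over time, the purpose written beside it is a PD 0332991 effect, and summary statistics do not test it. For cell cycle arrest the plan does better: section 1.9.1 explains why the pre-PD 0332991 Ki67 is needed, objective 3 in section 2.2 compares C1D1 with C1D15, and section 15.5 uses McNemar tests.

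A reader might go further and infer that the run-in will by itself make the result significant. The documents do not support that. Their evidence is preclinical, bears on cyclin D1 and pRb, and carries no effect size; nothing shows a run-in effect on p16, IL6, beta-galactosidase, pS6 or FOXM1. Section 1.9.4 describes arrest under PD 0332991 as different in kind from arrest under ER antagonists, and section 1.7 reports that RB phosphorylation persists in endocrine-resistant preclinical models. At a 0.25 SD shift, rejection is 14% to 27%.

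A reader might also extend the point to every cohort. In the endocrine resistant cohort the first scheduled trial tumor sample is already on endocrine therapy, so the point does not apply unless archival pre-treatment tissue is added as a time point.

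Finally, C1D15 minus C1D1 does not isolate the drug completely. It carries two further weeks of anastrozole without a concurrent control, and its 5% error rate above rests on the run-in effect being flat after C1D1.

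**Conclusion.** The point holds for the PIK3CA wild type and mutant cohorts. The time effect in section 15.6 answers a different question from the one in sections 1.9.4 and 1.9.5, and a significant result can come from anastrozole alone. If the run-in shift reaches about 0.5 SD of the paired difference at n=28, or 0.75 SD at n=15, the time test rejects in roughly three quarters or more of trials in which PD 0332991 does nothing. The size depends on a shift that the documents do not quantify, on complete data and on constant within-woman variance. The point does not reach the endocrine resistant cohort as scheduled. The objectives concerned are exploratory, with no decision rule, and the primary conclusion on complete cell cycle arrest is unaffected. It should be corrected because the correction is cheap and the mechanistic claim is part of the trial's stated goal.

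**What to change.** In section 15.6:

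1. Name the factors (patient and time) and list the time points for each marker and cohort, settling whether RB is assayed at surgery.
2. Make the within-woman C1D15 minus C1D1 contrast, from the same repeated-measures model, the inferential test of the PD 0332991 effect.
3. In the PIK3CA cohorts only, report C1D1 minus baseline separately as the anastrozole effect.
4. Where surgery is assayed, report surgery minus C1D15 as persistence, bringing into section 15.6 the comparison already named in section 1.9.4.
5. State that the overall time p-value is not evidence of a PD 0332991 effect, and that C1D15 minus C1D1 also includes two more weeks of anastrozole with no concurrent control.

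The samples, assays and model stay the same; the cost is a few sentences. Fewer markers may reach significance. For a 0.5 SD PD 0332991 change at n=28, power is about 72% against 76% for the time test if the change is seen at C1D15 only, and against 88% if it lasts to surgery.

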The relationship between *PIK3CA* mutation and responsiveness of ER+ breast cancers to CDK4/6 inhibitors has not been investigated. In preclinical studies, PD0332991 was found to be effective in a subpopulation of both *PIK3CA* mutant and wild type cancer [88]. The most promising predictors of response identified in preclinical studies have been the presence of intact Rb or down regulation of p16; however, this has not been confirmed in the recently reported clinical trial of letrozole in combination with PD 0332991 as first line therapy for metastatic ER+ breast cancer [22]. Since *PIK3CA* mutation is an important driver event in ER+ breast cancer, and direct inhibitors of PI3K, including those that target specifically the alpha catalytic subunit, are being developed to treat tumors with *PIK3CA* mutation, it is important to investigate the anti-tumor effect and predictors of response to PD 0332991 in *PIK3CA* wild type and mutant population separately.

The study was designed initially to focus on the population of ER+ breast cancer without *PIK3CA* hotspot mutations since trials of inhibitors against PI3K pathway, such as the NCI9170, were ongoing the same time for the population with *PIK3CA* hotspot mutations. As the NCI9170 trial that enrolls patients with *PIK3CA* mutant tumors is approaching its enrollment target as of November 2013, we plan to open the *PIK3CA* mutant cohort for this trial, starting in institutions that do not have NCI9170 open.

1.8 Rationale for Adding Adjuvant PD 0332991 in Combination with Anastrozole in Patients who Derived benefit from the Addition of PD 0332991 during Neoadjuvant Therapy (Amendment #7)

Between 4/23/2013 and 4/24/2015, the study enrolled 50 patients with clinical stage II or III ER+ HER2- breast cancer to the *PIK3CA* mutant and *PIK3CA* wild type (WT) cohorts. Of these 50 patients, 45 (*PIK3CA* WT, n=28; *PIK3CA* mutant, n=15; *PIK3CA* unknown, n=2) were evaluable for Ki67 analysis at C1D15 after completion of 6 weeks of anastrozole and 2 weeks of PD 0332991 (for the primary endpoint). The data was presented at 2015 SABCS {Ma, 2015 #3841}. Complete cell cycle arrest (CCCA) was achieved in 39 of the 45 (87%, 90% CI: 75-94%) evaluable patients, 22 of 28 (79%, 90% CI: 62-90%) patients

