in the PIK3CA WT cohort and all 15 (100%, 90% CI: 82-100%) patients in the PIK3CA mutant cohort. The study met its primary endpoint of achieving a CCCA rate of 66% in C1D15. In addition, 26 patients who did not achieve CCCA with anastrozole alone on C1D1 achieved complete CCCA in C1D15 post 2 weeks of combination therapy. These data justify the evaluation of PD 0332991 in the adjuvant setting. The international PALLAS (PALbociclib CoLlaborative Adjuvant Study) trial is currently enrolling patients with high risk ER+ HER2- breast cancer to receive 2 years of palbociclib (PD 0332991) in the adjuvant setting. However, patients who received neoadjuvant PD 0332991 (palbociclib) are not eligible for the adjuvant PALLAS trial. We therefore propose to include in this trial the option of adjuvant PD 0332991 with anastrozole for 23 cycles after chemotherapy and radiation therapy for those who derived benefit from PD 0332991 in the neoadjuvant setting in this trial. This includes:

- The 26 patients who achieved complete cell cycle arrest only after the addition of PD 0332991 (C1D1 Ki67 $>2.7\%$ and C1D15 Ki67 $\leq 2.7\%$) (in the PIK3CA WT, mutant, or unknown cohorts).
- Patients who have a Ki67 $\leq 10\%$ on C1D15 biopsy in the endocrine resistant cohort (including patients enrolled prior to activation of Amendment #7).

All patients (with the exception of those who withdraw consent for follow-up and those who did not undergo surgery) will be followed for invasive disease recurrence and overall survival for 5 years in the adjuvant setting or until recurrence (whichever comes first). Blood will be drawn for serum, plasma, and circulating cell-free DNA (cfDNA) yearly.

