12.3 Surgery

A pathologic complete response (pCR) is defined as no histology evidence of invasive tumor cells in the surgical breast specimen and sentinel or axillary lymph nodes.

All eligible women who have been begun treatment with combination therapy and have tumor Ki67 determined on C1D15 (or a subsequent cycle) are included in the analysis of complete cell cycle arrest. Women with tumor Ki67>2.7% on therapy are considered to have a non-complete cell cycle arrest.

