15.5 Data Analysis

All data analyses will be performed separately for each cohort unless otherwise specified.

Demographic and clinical characteristics of the sample, as well as response, toxicity by grade, and loss to follow-up will be summarized using descriptive statistics. The rate of complete cell cycle arrest will be calculated and the corresponding 90% confidence interval (CI) will be provided. The rates for pCR and PEPI 0 and their 90% CIs will also be calculated. The differences in overall survival (OS) and relapse-free survival (RFS) for patients with or without complete cell cycle arrest on C1D1 will be described using Kaplan-Meier product limit estimator and compared by log-rank tests. Similar analysis will be performed for complete cell cycle arrest on C1D15 or patients with or without PEPI 0, with the two cohorts combined or separately. A trajectory analysis (see below) will also be performed for this comparison.

Analysis of other secondary endpoints:

Clinical response rate: The clinical response rate will be estimated by the number of patients whose disease meets the WHO criteria of complete or partial response prior to surgery divided by the total number of eligible patients who began combination neoadjuvant treatment. A 90% confidence interval for the true clinical response rate will be calculated using the Duffy-Santner approach for the endocrine resistant cohort (2-stage design). The complete cell cycle arrest rates and the corresponding 90% confidence intervals will also be calculated for PIK3CA wild type and mutant cohorts separately and combined.

Radiological response rate: The radiological response rate will be estimated by the number of patients whose disease meets with WHO criteria for complete or partial response at the evaluation prior to surgery divided by the total number of eligible patients who began

combination neo-adjuvant therapy. A 90% confidence interval for the true radiographic response rate will be calculated using the Duffy-Santner approach. The analysis will be performed with the two cohorts separately and combined.

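### Section 15.6 tests markers of sensitivity and resistance only against undefined response groups, never against the measured Cycle 1 Day 15 Ki67, which costs power and can leave the mutant cohort without a test

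*Combined protocol and SAP*

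**What the plan says.** The paragraph of Section 15.6 on potential markers of sensitivity and resistance uses Cycle 1 Day 1 (C1D1) tumor. It sets two analyses. For expression: "The gene expression levels between responses will also be summarized using means, standard deviations, medians, and compared by t-test or Mann-Whitney rank-sum test", as appropriate. For gene copy number: "its association with clinical outcomes will also be assessed using contingency tables and fisher's exact test". It does not say which response or which clinical outcome is meant, and gives no significance level, effect size or power.

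Elsewhere the plan uses several response measures. Arrest is a cut of Ki67; Section 12.3 says: "Women with tumor Ki67>2.7% on therapy are considered to have a non-complete cell cycle arrest". Section 12.1 defines clinical and radiologic response by WHO criteria, Section 12.2 defines resistance by Ki67 above 10% or progression, and Section 12.3 defines pathologic complete response.

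Section 9.3.2 reports Ki67 as a continuous value, and Section 15.5 analyses its percent change on the log scale. The trajectory analysis in Section 15.5 relates Ki67 patterns to clinical outcomes, not to these markers.

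On cohorts, Section 15.5 says: "All data analyses will be performed separately for each cohort unless otherwise specified". Section 2.3 allows the exploratory objectives to be assessed in the mutant and wild-type cohorts either combined or separately, with the endocrine resistant cohort on its own.

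**The concern.** Exploratory objective 3 looks for mechanisms that affect tumor response to the combination, and Section 1.1 names biomarkers for patient selection as a product of the trial. A two-group test discards how far each tumor lies from the cut. It is weakest when one group is very small, and it cannot be computed when one group is empty. Both can happen here with arrest as the response. The measured C1D15 Ki67 comes from the same mandatory biopsies and has neither defect to the same degree. At stake is whether a moderate marker effect that these samples could show is missed, and whether the mutant cohort can say anything about markers on its own.

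**Working it through.** **1. Counts, reproduced.** Section 1.8 gives "22 of 28 (79%, 90% CI: 62-90%) patients" for wild type, "all 15 (100%, 90% CI: 82-100%) patients in the PIK3CA mutant cohort", and 39 of 45 overall. Exact (Clopper-Pearson) 90% intervals are 62.0-90.2% for 22/28, 81.9-100% for 15/15 and 75.4-94.0% for 39/45, all matching the stated figures.

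Non-arrest counts: wild type 28 − 22 = 6; mutant 15 − 15 = 0; all 45 − 39 = 6. So all six non-arrest tumors are wild type. The two women with unknown PIK3CA status both arrested (39 − 22 − 15 = 2). A combined test is therefore 39 v 6, or 37 v 6 without those two.

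**2. What a 22 v 6 t-test can detect.** The noncentrality is d / √(1/22 + 1/6), with 26 degrees of freedom. At a two-sided 5% level, d = 1.0 SD gives 55% power and d = 1.35 SD gives 81%. The marker must differ by about 1.35 SD for conventional power.

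**3. Power against measured Ki67.** These assumptions are not in the documents: marker and ln C1D15 Ki67 are bivariate normal with correlation ρ, the 6 highest of 28 Ki67 values form the non-arrest group, and the test is two-sided at 5%. From 60,000 simulations:

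| ρ | t-test, 22 v 6 | Pearson, ln Ki67 | Loss (points) | Mann-Whitney | Spearman | Loss (points) |
|---|---|---|---|---|---|---|
| 0.3 | 18% | 35% | 16 | 16% | 31% | 14 |
| 0.4 | 30% | 58% | 28 | 27% | 52% | 25 |
| 0.5 | 46% | 80% | 34 | 42% | 74% | 32 |
| 0.6 | 64% | 94% | 30 | 60% | 91% | 30 |

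Losses are from unrounded values. They shrink for strong effects: 17 points (t-test v Pearson) at ρ = 0.7 and 5 to 6 at ρ = 0.8.

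**4. Floor effect.** At least 79% of wild-type values are at or below 2.7%, so ties near the lowest reportable Ki67 are plausible. For ρ from 0.3 to 0.6:
- Lowest half tied: the t-test loses 8 to 19 points to Pearson, and Mann-Whitney loses 10 to 24 to Spearman.
- Lowest 70% tied: 2 to 5 points, and 6 to 14 for the rank tests.

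The continuous analysis was ahead in every case.

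**5. Other splits, no floor, ρ = 0.3 / 0.4 / 0.5 / 0.6.**
- Wild type at its design alternative (66% of 33, about 22 v 11): the t-test loses about 15 / 23 / 24 / 16 points to Pearson.
- Endocrine resistant cohort at its alternative (20% of 37, about 7 v 30): t-test 23 / 38 / 56 / 75%, Pearson 45 / 71 / 90 / 98%.
- All 45 women, 39 v 6: t-test 38% v Pearson 79% at ρ = 0.4, and 57% v 95% at ρ = 0.5.
- Mutant cohort, n = 15: no arrest test exists; Pearson has 33 / 50 / 71% at ρ = 0.4 / 0.5 / 0.6. These are optimistic, because all 15 values lie at or below 2.7%.

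**6. Adjusting for ln C1D1 Ki67.** With n = 28, an assumed C1D1-C1D15 correlation of 0.5, and ρ as above, power for the marker term is:
- marker uncorrelated with C1D1 Ki67: about 43 / 71 / 91 / 99%;
- marker correlated 0.3: about 15 / 35 / 61 / 86%;
- marker correlated 0.5: about 6 / 18 / 41 / 72%, which is below the t-test (18 / 30 / 46%) for ρ from 0.3 to 0.5.

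So adjustment can gain or lose power.

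**The case against.** *Response is not stated to be arrest.* This stands. The 22 v 6 and 15 v 0 splits follow from one reading of Section 15.6, and WHO response, pathologic complete response or Ki67-based resistance would give others. The lack of a definition is itself a gap.

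*The mutant women are not lost, because Section 2.3 permits a combined analysis.* This also stands, so a reader should not infer that they contribute nothing. But they enter only as arrest cases, so a marker associated with PIK3CA status would appear associated with arrest. Section 1.7.1 also wants predictors studied in the two populations separately.

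*The power loss depends on chosen assumptions.* It does. One might quote a single figure of 16 to 33 points, but the documents give neither ρ nor the Ki67 distribution, and a floor could remove most of the gain.

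*The split is judged after the results.* For wild type it is, but step 5 shows a loss of similar order at the design alternatives.

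*The arrested group mixes two drug effects.* Section 1.8 names 26 women who reached arrest only once PD 0332991 was added, so 39 − 26 = 13 arrested women fall outside that group. One might infer that those 13 responded to anastrozole alone. The documents do not say so; some may lack a C1D1 value. Nor does it follow that a C1D1-adjusted model should be the main test: it asks a different question, and step 6 shows that it can have less power than the planned t-test.

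*The analysis is exploratory and nothing forbids an added correlation.* True, and this limits the weight of the point.

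**Conclusion.** The point holds in this form. Section 15.6 specifies only group comparisons for its markers, leaves the groups undefined, and does not use a continuous outcome that the trial already measures. If response means arrest, the mutant cohort alone has no test, and the wild-type t-test gives up about 15 to 35 points of power against correlation with ln Ki67. That range assumes bivariate normality, ρ from 0.3 to 0.6, a two-sided 5% level and no floor. It falls to about 8 to 20 points with half the values tied at a floor and about 2 to 10 with 70% tied. The direction was the same in every unadjusted scenario examined; the size is not fixed by the documents. The primary endpoint and its decision rule are not affected.

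**What to change.** In Section 15.6:

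1. Define *responses* and *clinical outcomes* for the marker analysis.
2. Within each cohort, make the unadjusted Spearman correlation of each marker with C1D15 Ki67 the main exploratory test, or regression on ln C1D15 Ki67 with zeros set to the smallest reportable value. Enter copy number as its continuous log ratio.
3. Keep the response-group summaries and contingency tables as description.
4. Report a model adjusted for ln C1D1 Ki67 only as a supplementary analysis of the effect added by PD 0332991, and state that it answers a different question.
5. If a combined wild-type and mutant test by arrest is shown, state that the mutant women are all in the arrest group.

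The cost is a change of wording and a little more analysis; no new samples or assays are needed. The gain will be smaller if many Ki67 values are tied near the floor, so the number tied should be reported. Women without a C1D1 Ki67 drop out of the supplementary model only.
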